5.1.2 Study duration per subject

The study duration for each subject is estimated to be up to a maximum of 120 weeks:

- Open-Label Treatment Period: up to 100 weeks (~2 years)
- SFU Visit: 20 weeks after the final dose of bimekizumab

The subject may remain in the study until the study ends after 120 weeks, until the Sponsor decides to close the study, or until bimekizumab development is stopped by the Sponsor, whichever comes first. The Sponsor may consider transitioning the subject into another bimekizumab study or program.

The end of the study is defined as the date of the last visit of the last subject in the study.

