## 2 PROTOCOL SUMMARY

PA0009 is a multicenter, open-label extension (OLE) study evaluating the long-term safety, tolerability, and efficacy of bimekizumab (also known as UCB4940) in subjects with psoriatic arthritis (PsA). Only subjects who complete PA0008, a Phase 2b study, are eligible for enrollment into PA0009. At Week 48 of PA0008, all subjects continuing into PA0009 will undergo the final PA0008 study assessments and any nonoverlapping PA0009 entry assessments and will then receive their first open label dose of bimekizumab.

PA0008 was a multicenter, Phase 2b, randomized, double blind, placebo-controlled, parallel group, dose ranging study to evaluate the efficacy and safety of bimekizumab in 200 subjects with active PsA.

In the PA0009 OLE study, bimekizumab will be administered at a dose of 160mg every 4 weeks (Q4W) subcutaneously (sc) for all subjects regardless of treatment received in PA0008.

Up to 200 subjects from PA0008 may be enrolled into this study at any of the sites participating in PA0008.

The study duration for each subject is estimated to be up to a maximum of 120 weeks: an Open Label Treatment Period of up to 100 weeks (~2 years), followed by a Safety Follow up (SFU) Visit 20 weeks after the final dose of bimekizumab.

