**Table 3-2: Treatment sequence assignment for safety summaries**

Sequence	BKZ 160mg	BKZ 320mg	BKZ Total
Placebo/BKZ 160mg/BKZ 160mg	X		X
Placebo/BKZ 320mg/BKZ 160mg	X	X	X
BKZ 16mg/BKZ 160mg/BKZ 160mg	X		X
BKZ 16mg/BKZ 320mg/BKZ 160mg	X	X	X
BKZ 160mg LD/BKZ 160mg/BKZ 160mg	X		X
BKZ 160mg/BKZ 160mg/BKZ 160mg	X		X
BKZ 320mg/BKZ 320mg/BKZ 160mg	X	X	X

BKZ=bimekizumab; LD=loading dose.

- For all safety summaries, subjects who took bimekizumab 320mg during PA0008 will contribute to all 3 columns. Subjects who did not take 320mg in PA0008 will contribute to the ‘BKZ 160mg’ and ‘BKZ Total’ columns.
- The combined summaries will include all data from PA0008 in addition to PA0009 only for subjects who were enrolled in PA0009.
- The PA0009 only summaries will include only data collected in PA0009 (unless otherwise stated).

Subjects will be summarized based on the actual/received treatment or the planned treatment for different analysis sets as follows:

- ES: planned treatment.
- SS and SS Sub-populations: actual treatment.
- FAS: planned treatment.

For actual and planned treatments in PA0008, the data will be used directly from the PA0008 analysis database without any rederivation of treatment assignments in each period.

In PA0009 it will be assumed that all subjects received the correct treatment as the dose level of bimekizumab is the same for all subjects and throughout the study (160mg). If a subject missed a dose at PA0008 Week 48, they will also be considered to have received the planned treatment. Thus for all subjects in PA0009, the actual treatment will be the same as the planned treatment.

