- Action taken with IMP: dose not changed, dose reduced, dose increased, drug temporarily, interrupted, drug permanently withdrawn or not applicable.
- Outcome: resolving, not resolved, resolved, resolved with sequelae, worsened, fatal or unknown.

AEs (including SAEs) are characterized as either non-treatment-emergent or treatment emergent according to the following criteria:

- Non-treatment emergent AEs are those with onset date after a 140-day period after the end date of study medication.
  - Any AE occurring more than 140 days after the last administration of study medication in PA0008 and prior to the first administration of study medication in PA0009 will also be considered as non-treatment emergent, and will therefore be excluded from the summary tables. Such events will be included in the listings.
- TEAEs are those with onset date on or after the start date of study medication in PA0009.
- Events that were ongoing at the end of PA0008 will have their treatment-emergent status taken from the PA0008 database.

For all AEs the following variables will be calculated (see [Section 10.2.1](#)):

- Duration.
- Time since first bimekizumab dose.
- Time since last/latest bimekizumab dose.

AE summaries will, in general, include only events with onset on or after the start date of study treatment in PA0009. Certain displays will be repeated including all AEs in PA0008 (with the exception of those with onset during placebo treatment) and PA0009 as outlined below. These displays will include only subjects from PA0008 who were enrolled in PA0009.

In general, the attributes of these events (for AEs that started and were resolved in PA0008) will be taken from the PA0008 database. However, the identification of Safety Topics of Interest will be made across all events in PA0008 and PA0009 using the criteria defined in this SAP.

For events which were ongoing at the end of PA0008, the following rules will be implemented:

- Onset date (and derived variables) will be taken from the PA0008 database
- End date, outcome, actions taken and seriousness will be taken from the PA0009 database.
- In order to ensure that AEs are not duplicated in the outputs these will be merged across the studies by Subject ID, verbatim term (AETERM), dictionary-derived term (AEDECOD), start date (AESTDTC), relationship (AEREL) and severity (AESEV) to create one record for the specific event.

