Summaries of AEs in PA0008 and PA0009 combined will include AEs with onset on the first dose of bimekizumab in PA0008 up to 140 days after the last dose of bimekizumab in PA0009. AEs which occur on the day of a treatment switch will be considered to have begun on the previous treatment, with the exception of the following AEs which will be considered to have begun on the new treatment:

- Events that fulfill the anaphylaxis criteria for acute events (see [Section 10.2.3](#)).
- Events that fulfill the hypersensitivity reaction criteria for (see [Section 10.2.3](#)).
- Events with a HLT of “Administration site reactions NEC”.
- Events with an HLT of “Injection site reactions”.

AEs that occur on the first day of bimekizumab treatment in PA0008 following initial treatment with placebo will not be included in the summaries, unless they fulfill 1 of the 4 exception criteria above. AEs that occur after the last dose of bimekizumab in PA0009 and up to 140 days after the last dose of bimekizumab in PA0009 will be assigned to bimekizumab 160mg.

AEs will be presented as “number of subjects (percentage of subjects) [number of events]”. “[number of events]” will include all cases of an AE including repeat occurrences in individual subjects, while “number of subjects” will count each subject only once.

An overview of TEAE (number and percentage of subjects with any TEAE, serious TEAE, TEAE leading to study discontinuation, TEAE leading to permanent withdrawal of study medication, drug-related TEAE, severe TEAE, fatal AE [see note below], fatal TEAE and TEAE

with missing seriousness) will be provided by treatment group at completion of PA0008 and overall. This summary will be repeated by SS Sub-population.

This table will be repeated including all TEAEs in PA0008 and PA0009 reported for subjects in the PA0009 SS (with the exception of those with onset during placebo treatment) combined. The 'BKZ 160mg' treatment column in this table will include subjects in both the BKZ 160mgLD and BKZ 160mg treatment groups.

The category for fatal AEs will be based on all subjects enrolled in PA0009 in all the above summaries.

The following categories of TEAE will be summarized by MedDRA SOC, HLT and PT including EAIR and EAER (calculated as described in [Section 10.2.2](#)), where all summaries refer to AEs reported in PA0009 only except where stated:

- All TEAEs by treatment group at completion of PA0008 and overall.

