An additional table will be presented by MedDRA SOC, HLT and PT, by treatment at time of AE onset (BKZ 160mg, BKZ 320mg and BKZ Total) for all TEAEs in PA0009 and all TEAEs that were ongoing from PA0008 at the time of the PA0009 EV. Ongoing TEAEs are defined as TEAEs that started prior to the PA0009 EV and continued after the first dose of study medication in PA0009. The 'BKZ 160mg' treatment column in this table will include subjects in both the BKZ 160mgLD and BKZ 160mg treatment groups.

TEAEs classified as Safety Topics of Interest and associated tables are defined in [Section 10.2.3](#).

The following AE listings will be provided based on the ES:

- Glossary table for all AEs (this listing will include all events in PA0008 and PA0009 for subjects that were enrolled in PA0009 [with the exception of AEs with onset during placebo treatment]).
- All AEs (this listing will include all events in PA0008 and PA0009 for subjects that were enrolled in PA0009 [with the exception of AEs with onset during placebo treatment]).
- All SAEs (this listing will include all events in PA0008 and PA0009 for subjects that were enrolled in PA0009 [with the exception of AEs with onset during placebo treatment]).
- All AEs leading to study discontinuation.
- All deaths.

The following listings will be provided based on the SS:

- Serious infections TEAEs.
- Fungal infectious disorder TEAEs.
- Opportunistic infection (including tuberculosis) TEAEs.
- Malignant or unspecified tumor TEAEs.
- Malignant tumor TEAEs.
- Adjudicated cardiovascular TEAEs by event type.
- Adjudicated cardiovascular TEAEs by event type for major adverse cardiac events (MACE)
- Adjudicated cardiovascular TEAEs by event type for extended MACE
- TEAEs identified for potential review by the Cardiovascular Event Adjudication Committee.

- Neutropenia TEAEs.
- Suicidal ideation and behavior TEAEs.
- TEAEs identified for potential review by the Neuropsychiatric Adjudication Committee.
- TEAEs adjudicated by the Neuropsychiatric Adjudication Committee.
- Inflammatory bowel disease TEAEs.
- Hypersensitivity reaction TEAEs.
- Anaphylactic reaction TEAEs.
- Hepatic events TEAEs.
- Hospitalization/Emergency Room Visits.

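### In the SAP 10.2 table that joins PA0009 TEAEs to TEAEs ongoing from PA0008, splitting by treatment at onset makes the 160mg and 320mg columns non-comparable

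*SAP*

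**What the plan says.** SAP 10.2 (Adverse events) adds one table by SOC, HLT and PT, with columns "by treatment at time of AE onset (BKZ 160mg, BKZ 320mg and BKZ Total) for all TEAEs in PA0009 and all TEAEs that were ongoing", meaning those begun in PA0008 and still present at the entry visit. It fixes which PA0008 events qualify: "Ongoing TEAEs are defined as TEAEs that started prior to the PA0009 EV and continued after the first dose of study medication in PA0009". PA0008 events that had resolved before then are therefore left out.

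Four other rules determine what each column contains:

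- **Dose in PA0009.** SAP 2 says "bimekizumab will be administered at a dose of 160mg every 4 weeks (Q4W) subcutaneously (sc) for all subjects regardless of treatment received in PA0008". SAP 3.7 treats actual and planned treatment as identical in PA0009 because "the dose level of bimekizumab is the same for all subjects and throughout the study (160mg".
- **Event window.** SAP 10.2: "TEAEs are those with onset date on or after the start date of study medication in PA0009", and "Non-treatment emergent AEs are those with onset date after a 140-day period after the end date of study medication".
- **Events after the last dose.** In the combined-study rules of SAP 10.2, those occurring "up to 140 days after the last dose of bimekizumab in PA0009 will be assigned to bimekizumab 160mg".
- **Switch-day events.** The same rules assign an event starting on the day of a treatment switch to the previous treatment. The exceptions are acute anaphylactic, hypersensitivity, administration-site and injection-site events.

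The text for this table mentions no exposure adjustment, no separation of ongoing from new events, and no caution about comparing columns.

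**The concern.** The table combines two kinds of event and then divides them by a variable that nearly separates the two kinds. Nobody takes 320mg after entry, so the 320mg column has almost no way to acquire a new event. It shows what was left over at one moment, selected on not having resolved. The 160mg column is mainly incidence over the whole extension, and it includes new events in subjects who finished PA0008 on 320mg.

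The columns carry dose labels and stand side by side at preferred-term level, in a study whose primary objective is safety. With no true difference between doses, the lower dose would appear to have far more adverse events, and short events such as acute infections would almost vanish under 320mg. The same column labels are used in the tables that combine all PA0008 and PA0009 events, so a reader could meet two tables with identical headings and very different 320mg figures.

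**Working it through.** **The plan's own window.** Protocol 5.1.2 gives "Open-Label Treatment Period: up to 100 weeks (~2 years", with follow-up 20 weeks after the final dose. In days: 100 × 7 + 140 = 840, and 840 / 7 = 120 weeks. This reproduces the stated maximum study duration and is the longest period over which new events enter the 160mg column.

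**Time on 320mg before entry.** The sequences in SAP 3.7 give T = 36 weeks (placebo or 16mg for 12 weeks, then 320mg to Week 48) or T = 48 weeks (320mg throughout PA0008).

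**Assumptions, since the documents give neither event rates nor durations.** The true event rate λ is the same and constant on both doses; event duration is exponential with mean d weeks; each subject is observed for the full 120 weeks; and 70% of subjects have at least one PA0009 TEAE.

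**Rate.** 1 − exp(−120λ) = 0.70, so λ = 1.204 / 120 = 0.01003 per week.

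**320mg column if every 320mg-onset event were counted.** The share of subjects is 1 − exp(−λT).
- T = 36: 1 − exp(−0.361) = 30%
- T = 48: 1 − exp(−0.482) = 38%

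**320mg column under the table's rule.** Expected events still ongoing at entry, per subject, are λd(1 − exp(−T/d)). The share of subjects is 1 − exp(−that value). The share of 320mg events left out is 1 − d(1 − exp(−T/d))/T.

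| Mean duration d | Events left out (T = 36 / 48) | 320mg column, ongoing only (T = 36 / 48) |
|---|---|---|
| 3 weeks | 92% / 94% | 3.0% / 3.0% |
| 12 weeks | 68% / 75% | 10.8% / 11.1% |
| 26 weeks | 46% / 54% | 17.8% / 19.7% |

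For example, with d = 12 and T = 36: 12 × (1 − exp(−3)) = 11.40 weeks; 0.01003 × 11.40 = 0.114; 1 − exp(−0.114) = 10.8%.

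**Separating the two effects.** The 160mg column shows at least 70%, because ongoing 160mg-onset events come on top. Of the gap between 70% and 3-11%, the step from 70% down to 30-38% comes from 36 or 48 weeks of observation instead of 120. The step from 30-38% down to 3-11% (d of 3 to 12 weeks) comes from leaving out resolved events, and only this step is specific to the table's inclusion rule.

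**Sensitivity.**
- If no event ever resolved, the 160mg column would still carry 120/48 = 2.5 to 120/36 = 3.3 times as many events per subject. The direction in crude counts therefore does not depend on d.
- If the switch-day rule applies here, the 320mg column gains about one day of events. With d = 3 its share moves from 3.0% to 3.1%.
- Dividing by exposure would not repair the column. For d = 12, ongoing events over 320mg exposure give a 320mg/160mg event-rate ratio of 11.40/36 = 0.32 or 11.78/48 = 0.25 when the true ratio is 1.

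**The case against.** The strongest reply is that this is an additional descriptive table in a single-arm extension, with no test between columns and nothing in the SAP calling it a dose comparison. Carried-over events have to be captured and followed, so a display of the adverse-event burden in PA0009 that includes them is reasonable. SAP 10.2 separately plans all TEAEs and serious TEAEs across both studies by treatment at onset, with EAIR and EAER, and SAP 10.1 defines 320mg time at risk for them. The resolved events missing here are counted there and appear in the all-AE listing.

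Most of that stands. No safety information is lost, and a sound by-dose display is already specified. A reader might infer that the plan as a whole makes 320mg look safer, or that the full contrast of 3-11% with 70% is produced by this table's construction. The documents support neither reading: the complete tables exist, and part of the contrast is observation time, which affects crude percentages in any by-onset table. Nor is it strictly true that the 320mg column holds only unresolved events, because the switch-day rule, if applied, adds most entry-day events in 320mg completers.

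What the reply does not answer is that this table, as written, still puts dose labels on a prevalence and an incidence with nothing to warn the reader.

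There is also a fair objection to moving the whole table to treatment group at completion of PA0008. An event that began on 16mg and is still ongoing would then sit in a 160mg or 320mg column, whereas SAP 3.7 sends 16mg-period events to the Total column only.

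**Conclusion.** The point holds for this one supplementary table. That the columns are not comparable follows from the SAP's own rules and needs no assumption; that the crude figures lean towards 320mg follows once true rates are equal. The size of the effect does rest on assumptions: a 70% PA0009 incidence, exponential durations and full 120-week observation. On those, the inclusion rule lowers the 320mg column from about 30-38% to about 3-11% for mean durations of 3 to 12 weeks, and to about 18-20% at 26 weeks. The conclusion does not extend to the combined-study tables or to the primary safety summaries. It is worth correcting because safety is the primary objective, but it is a matter of presentation in one table.

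**What to change.** In SAP 10.2, divide this table into two labelled blocks:

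- **(a) TEAEs with onset in PA0009**, by treatment group at completion of PA0008 and overall, as in the other PA0009 tables.
- **(b) TEAEs ongoing at the PA0009 entry visit**, by treatment at onset, labelled as prevalence at entry. Use the number of subjects on each dose in PA0008 as denominator, and count 16mg-onset events in BKZ Total only.

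Add a footnote that the blocks must not be pooled to compare doses, and that the by-dose comparison is in the combined PA0008 and PA0009 tables with EAIR and EAER. State whether the switch-day rule applies to this table.

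The cost is a short SAP edit and a small change to one table shell. Block (a) repeats counts already planned, and dose attribution is kept for the carried-over events. No new data are needed.

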### 10.2.1 Adverse event duration and time since first/last dose

Missing start or end dates will be imputed as described in [Section 4.2.3](#) prior to any calculation described in this section.

The duration of each AE will be calculated as:

$$\text{Duration (days)} = \text{date of outcome} - \text{date of onset} + 1 \quad (18)$$

The time since first bimekizumab dose for each TEAE will be calculated three times:

- Relative to the date of first administration of bimekizumab in PA0008.
- Relative to the date of the first dose of bimekizumab 160mg or 160mgLD, only for AEs with onset during treatment with bimekizumab 160mg or 160mg LD OR
- Relative to the date of the first dose of bimekizumab 320mg, only for AEs with onset during treatment with bimekizumab 320mg.
  - For these criteria during treatment refers to TEAEs with onset up to 140 days after the last dose on that treatment.
- Relative to the start date of study medication in PA0009.

Time since first dose will be calculated as follows for AEs occurring on or after the reference date (as defined above):

$$\begin{aligned} \text{Time since first BKZ dose (days)} \\ = \text{Date of onset} - \text{Reference date} + 1 \end{aligned} \quad (19)$$

The time since most recent bimekizumab dose for each TEAE will be calculated as follows for AEs occurring on or after the reference date (as defined above):

$$\begin{aligned} \text{Time since most recent BKZ dose (days)} \\ = \text{Date of AE onset} \\ - \text{Date of most recent dose prior to AE} + 1 \end{aligned} \quad (20)$$

For any AE occurring on the same day as a given dosing occasion the most recent dose will be considered to be the dose given on the same day ie, time since most recent dose would be equal to 1 for all such AEs.

For AEs occurring prior to the reference date (as defined above) the time since dosing will be calculated as follows for first/most recent BKZ dose:

$$\text{Time since BKZ dose (days)} = \text{Date of AE onset} - \text{Reference date} \quad (21)$$

Days on treatment at AE onset will be calculated three times using the same three reference dates as for time since first dose. Days on treatment at AE onset will be calculated as:

$$\begin{aligned} \text{Days on treatment at AE onset} \\ &= \text{Date of last or latest dose prior to AE onset} \\ &- \text{Reference date} + 1 \end{aligned} \quad (22)$$

As above, for any AE occurring on the same day as a given dosing occasion the last or latest dose prior to AE onset will be considered to be the dose given on the same day as the event.

For AEs occurring prior to the reference date, the days on treatment will be 0.

### 10.2.2 Exposure-adjusted incidence rate and exposure-adjusted event rate

The time at risk (in days) at AE onset is the same as the time since first bimekizumab dose as described in [Section 10.2.1](#).

Total time at risk (as defined in [Section 10.1](#)) and time at risk at AE onset will be divided by 365.25 to give years at risk.

EAIR and EAER will be calculated separately for tables including all events in PA0008 and PA0009 combined, and for tables including events with onset in PA0009 only. The former tables will use time at risk relative to the start date of bimekizumab 160mg/160mgLD or 320mg (for the 'BKZ 160mg' [this includes both BKZ 160mg and BKZ 160mgLD] and 'BKZ 320mg' columns) and time at risk relative to the date of the first dose of bimekizumab (for the 'BKZ Total' column). The latter table will use time at risk relative to the start date of study medication in PA0009.

The EAIR is defined as the number of subjects with a specific AE adjusted for exposure and will be scaled to 100 subject-years:

$$EAIR = 100 * \frac{n_{AE}}{\sum_{i=1}^{n_{AE}} T_{Exp,i} + \sum_{j=1}^{n_{noAE}} T_{Risk,j}} \quad (23)$$

where  $n_{AE}$  is the number of subjects with the AE,  $T_{Exp,i}$  is a subject's time at risk at AE onset in years (equation [16] in years) and  $T_{Risk,j}$  is the total time at risk in years for subjects who did not experience the AE of interest.

If a subject has multiple events at the level of coding evaluated, the time at risk at AE onset is calculated from the first occurrence of the AE.

Exact Poisson 95% CIs for incidence rates are calculated using the relationship between the Poisson and the chi-square distribution (Ulm, 1990; Fay and Feuer, 1997):

$$LCL = \frac{\chi_{2n, \frac{\alpha}{2}}^2}{2} \quad (24)$$

$$UCL = \frac{\chi_{2(n+1), 1-\alpha/2}^2}{2} \quad (25)$$

$$CI_{Lower} = 100 * \frac{LCL}{\sum_{i=1}^{n_{AE}} T_{Exp,i} + \sum_{j=1}^{n_{noAE}} T_{Risk,j}} \quad (26)$$

$$CI_{Upper} = 100 * \frac{UCL}{\sum_{i=1}^{n_{AE}} T_{Exp,i} + \sum_{j=1}^{n_{noAE}} T_{Risk,j}} \quad (27)$$

where  $n_{AE}$  is the number of subjects with the AE and is the basis for the number of the degrees of freedom for the chi-square quantile for the upper tail probability  $\chi^2$ ,  $T_{Exp,i}$  is a subject's time at risk at AE onset in years,  $n_{noAE}$  is the number of subjects without the AE and  $T_{Risk,j}$  the total time at risk for subjects who did not experience the AE.

The EAER is defined as the number of AEs reported up to 140 days after last dose, including repeat occurrences in individual subjects, and adjusted for exposure, and will be scaled to 100 subject-years:

$$EAER = 100 * \frac{N_{AE}}{\sum_{j=1}^{n_{All}} T_{Risk,j}} \quad (28)$$

where  $N_{AE}$  is the total number of AEs,  $T_{Risk,j}$  is a subject's total time at risk in years and  $n_{All}$  the number of subjects.

No CI will be computed for EAER.

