^f Assessment will be performed at Week 48 of the lead-in study PA0008 and will be used as the PA0009 entry value.

^g At PA0009 study entry collect pulse and BP prior to drug administration and then at 30 minutes and 1 hour after dosing. At all other visits collect pulse and BP prior to drug administration and once after dosing.

^h Includes evaluation of signs and symptoms of active TB and risk for exposure to TB.

ⁱ If the BSA affected by PSO was $\geq 3\%$ at Baseline of PA0008, determine the PASI.

^j If there has been a delay in menses, perform a urine pregnancy test.

[figure not shown]
^k All blood samples are to be taken prior to dosing.

^l It is recommended that the QuantiFERON TB Test be performed. This assessment will be performed at study entry, unless an IGRA negative result is available from less than 6 weeks prior to the first dose of open-label bimekizumab.

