**Table 10-2: Exposure time at risk**

Exposure Category	Start Date	End Date	Duration of Exposure
Total BKZ exposure	First dose of BKZ in PA0008	Last dose of BKZ in PA0009	Minimum of (End date – start date + 140 a ) and (Date of last clinical contact b – start date + 1)
Total exposure to BKZ 160mgLD and 160mg	First dose of BKZ 160mgLD or 160mg in PA0008 or PA0009	Last dose of BKZ 160mg in PA0009	Minimum of (End date – start date + 140 a ) and (Date of last clinical contact b – start date + 1)
Exposure to BKZ 320mg	First dose of BKZ 320mg in PA0008	First dose of BKZ 160mg in PA0009 for subjects who were dosed in PA0009 c .  Last dose of BKZ 320mg in PA0008 for subjects who were not dosed in PA0009	(End date – start date + 1) for subjects who were dosed in PA0009.  Minimum of (End date – start date + 140 a ) and (Date of last clinical contact b – start date + 1) for subjects who were not dosed in PA0009.
Exposure to BKZ 160mg in PA0009	First dose of BKZ 160mg in PA0009	Last dose of BKZ 160mg in PA0009	Minimum of (End date – start date + 140 a ) and (Date of last clinical contact b – start date + 1)

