- All TEAEs by treatment group at completion of PA0008 and overall, by SS Sub-population.
- Serious TEAEs by treatment group at completion of PA0008 and overall.
- Serious TEAEs by treatment group at completion of PA0008 and overall, by SS Sub-population.
- All TEAEs in PA0008 and PA0009 by treatment at time of AE onset (BKZ 160mg, BKZ 320mg and BKZ Total).
  - The 'BKZ 160mg' treatment column in this table will include subjects in both the BKZ 160mgLD and BKZ 160mg treatment groups.
- Serious TEAEs in PA0008 and PA0009 by treatment at time of AE onset (BKZ 160mg, BKZ 320mg and BKZ Total).
  - The 'BKZ 160mg' treatment column in this table will include subjects in both the BKZ 160mgLD and BKZ 160mg treatment groups.
- All TEAEs by timing of onset relative to ADAb status in PA0009. This will include columns for the following (regardless of PA0008 Baseline ADAb status):
  - TEAEs starting before the first ADAb positive result in PA0009 including the PA0009 EV (includes ADAb Categories 2a, 4a and 5a).
  - TEAEs starting on the same date or after the first ADAb positive result in PA0009 including the PA0009 EV (includes ADAb Categories 2a, 4a and 5a).
  - TEAEs for subjects who are ADAb negative at all time points in PA0009 including the PA0009 EV (includes ADAb Categories 1a and 3a).

The following categories of TEAE will be summarized by MedDRA SOC, HLT, and PT, by treatment group at completion of PA0008 and overall:

- TEAEs leading to study discontinuation and/or permanent withdrawal of study medication.
- TEAEs leading to permanent withdrawal of study medication.
- TEAEs with a fatal outcome.

- All TEAEs by maximum relationship.
- Serious TEAEs by maximum relationship.
- TEAEs with a fatal outcome by maximum relationship.
- All TEAEs by maximum intensity.
- Non-serious TEAEs reported by more than the reporting threshold of 5% of subjects. The cut-off will be applied before rounding on each treatment group and overall.

A further summary will be presented by treatment group at completion of PA0008 and overall displaying the frequency of TEAEs by descending frequency of PT.

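### The TEAE table by timing of first ADAb positivity splits events at the first positive sample but not person-time, so its before and after rates are understated

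*SAP*

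**What the plan says.** SAP 10.2 introduces a list of tables with the words "The following categories of TEAE will be summarized by MedDRA SOC, HLT and PT including EAIR and EAER (calculated as described in" Section 10.2.2). The list includes "All TEAEs by timing of onset relative to" ADAb status in PA0009, with three columns:

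- TEAEs starting before the first positive result (Categories 2a, 4a, 5a);
- TEAEs starting on that date or later (the same three categories);
- TEAEs in subjects negative throughout (Categories 1a, 3a).

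The time at risk comes from these places:

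- SAP 10.2.2, origin for PA0009-only tables: "The latter table will use time at risk relative to the start date of study medication in PA0009".
- SAP 10.2.2, subjects with the event (EAIR, equation 23): "The time at risk (in days) at AE onset is the same as the time since first bimekizumab dose as described in" Section 10.2.1, which for these tables runs from the first PA0009 dose. Subjects without the event contribute their total time at risk.
- SAP 10.2.2, EAER (equation 28): the quantity summed over all subjects "is a subject's total time at risk in years and" is not cut at any ADAb date.
- Table 10-2, row "Exposure to BKZ 160mg in PA0009": first to last dose plus 140 days, capped at last clinical contact.

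Two further statements fix the position of subjects positive at EV. Protocol Table 5-1, footnote k: "All blood samples are to be taken prior to dosing". SAP 10.2: "TEAEs are those with onset date on or after the start date of study medication in PA0009".

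**The concern.** An ADAb-positive subject can contribute events to both the before and the after column, but can be at risk of an event in only one of them on any given day. Under the rules above, EAER puts that subject's whole PA0009 time into both denominators. EAIR does the same for subjects without the event. For a subject whose event falls after positivity, EAIR also counts the time before positivity.

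Subjects positive at EV are a special case. Their sample precedes the first dose and TEAEs begin at the first dose, so they cannot have a before event, yet they add their full time to that denominator. Their after denominator is correct.

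The never-positive column has correct denominators. Comparing it with an understated after column therefore tends to hide harm associated with antibodies. The before-to-after comparison is driven by when the positive sample happened to be taken. The confidence limits (equations 26 and 27) use the same denominators and give no warning.

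Two smaller points concern the same displays. Categories 6a and 9a (some samples missing, the rest negative) fall in no column of this table. In the ACR50-over-time figures of SAP 9.2, a subject with one positive sample and all others missing is classed as ADAb negative, while a subject with no positive and two or more missing samples is classed as Missing.

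**Working it through.** The plan states no rate for this table, so there is no figure to reproduce. The denominator can be checked: last dose at Week 100 is 700 days, and 700 + 140 = 840 days = 120 weeks, which matches the stated maximum study duration.

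**Inputs from the documents.** T = 840 days (2.30 years) for a completer. ADAb samples are scheduled at EV, Weeks 12, 24, 36, 48, 72, 96 and 104, and SFU (SAP 2.2.5).

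**Assumptions.** Constant rate of 20 TEAEs per 100 patient-years (λ = 0.2 per year); all subjects complete; first positives spread evenly over Weeks 12, 24, 36, 48, 72 and 96.

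**EAER.** With first positivity at day s and no ADAb effect, the SAP rate divided by the true rate is s/T before and (T − s)/T after, whatever the constant rate.

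| First positive | Before / true | After / true | EAER printed (true 20.0) |
|---|---|---|---|
| EV | no event possible | 1.0 | after 20.0 |
| Week 12 | 0.1 | 0.9 | 2.0 and 18.0 |
| Week 24 | 0.2 | 0.8 | 4.0 and 16.0 |
| Week 48 | 0.4 | 0.6 | 8.0 and 12.0 |
| Week 72 | 0.6 | 0.4 | 12.0 and 8.0 |
| Week 96 | 0.8 | 0.2 | 16.0 and 4.0 |

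With no true effect, the printed after-to-before ratio runs from 9.0 (Week 12) to 0.25 (Week 96).

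Base case: mean s = (12 + 24 + 36 + 48 + 72 + 96)/6 = 48 weeks = 336 days.

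- No effect: before 20 × 336/840 = 8.0; after 20 × 504/840 = 12.0; never-positive 20.0.
- True doubling after positivity: after 40 × 504/840 = 24.0. Against never-positive this is a ratio of 1.2 instead of 2.0; against before it is 24.0/8.0 = 3.0 instead of 2.0.
- With 30% positive at EV: mean s = 0.7 × 336 = 235.2 days. No effect gives 5.6 and 14.4; doubling gives 5.6 and 28.8.

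**EAIR.** This takes the first onset within each column, with exponential onset times.

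- Before: expected events 1 − exp(−λs); correct time (1 − exp(−λs))/λ; the SAP adds exp(−λs)(T − s), from subjects without a before event.
- After: expected events 1 − exp(−λ(T − s)); correct time (1 − exp(−λ(T − s)))/λ; the SAP adds s for every subject.

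Averaged over the six visits, the SAP rules give 100 × 0.1631/2.019 = 8.1 before and 100 × 0.2365/2.103 = 11.2 after. Person-time split at the first positive sample returns 20.0 in both columns.

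**Confidence intervals.** In 20,000 simulated studies with 50 ADAb-positive subjects, none positive at EV and no effect, the SAP's 95% interval for EAIR covers the true 20 in about 17% (before) and 46% (after). Split person-time gives 97% and 96%. Going from 30 to 80 subjects, the SAP's coverage falls from 37% to 3% before and from 72% to 22% after.

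**Comparison within the SAP.** For the COVID-19 tables, where a subject can also appear in two columns, SAP 10.2.4 and Table 10-5 calculate time at risk separately for each period. The ADAb table has no counterpart.

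**The case against.** The SAP never writes out a denominator for the ADAb columns, so this could be called an omission that the programmers would repair. But SAP 10.2 sends the table to 10.2.2, and 10.2.2 has an explicit rule for tables of PA0009 events. Following that rule gives wrong rates.

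The direction for EAIR is less absolute than for EAER. Section 10.2.2 takes onset from the first occurrence without saying whether that is per column. If a pre-positive onset were used for a subject counted in the after column, that subject's time would be too short. On average the after rate is still understated: simulation under that reading gives 20% to 99% of the true rate, for rates of 5 to 300 per 100 patient-years. The before bias in EAIR also shrinks for very common terms, because it comes only from subjects without a before event.

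The size depends on the assumed timing. Spreading first positives over all nine sampling times gives about 9.5 and 10.5 instead of 8.0 and 12.0. With 30%, 50% or 75% positive at EV, coverage in the after column rises to 74%, 86% or 94%, while coverage before gets worse. Poor coverage is a feature of frequent terms and aggregate rows: at 5 per 100 patient-years it is about 67% and 85%, and at 2 per 100 it is near 100% in both columns. The point estimates stay biased at every rate.

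It is also fair that the protocol does not ask for this table, that nothing is tested, and that subject and event counts appear beside the rates. That limits the weight of the point. It does not make the printed rates comparable.

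**Conclusion.** The concern holds: the rates in this table are wrong as specified. EAER is understated before and after positivity by factors fixed by the timing of the first positive sample, except after positivity for subjects positive at EV. EAIR is understated on average. In the base case a true rate of 20 prints as 8.0 and 12.0 (EAER) or 8.1 and 11.2 (EAIR), and a true doubling against never-positive subjects prints as a ratio of 1.2. These sizes rest on assumed rates, completion and positivity timing; the direction for EAER does not depend on them. The primary safety tables are unaffected. The change should still be made, because this is the SAP's TEAE table by ADAb status and immunogenicity is one of the study's other objectives. The points on Categories 6a/9a and the ACR50 figures match the text but are secondary.

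**What to change.** Add a rule for this table to SAP 10.2.2, modelled on Table 10-5:

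- **Before:** time at risk from the first PA0009 dose to the day before the first positive sample. Subjects positive at EV contribute none.
- **After:** time at risk from the first positive sample, or from the first PA0009 dose if positive at EV, to the end of time at risk in Table 10-2.
- Measure time to onset from the start of the relevant period, take the first occurrence within that period, and use these times in equations 23 and 26 to 28.

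In the same edit:

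- Show Categories 6a and 9a in a separate column, or give their number in a footnote.
- In the ACR50 figures, report subjects with one positive and all other samples missing separately or in a sensitivity display, and do not count them as negative.
- Correct the cross-reference in 10.2.2 to equation 16, which is the PsAID-9 score. Time since first dose is equation 19.

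The cost is SAP wording and modest programming. No new data are needed.
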